6.5. Physical and Neurological Examinations

A complete PE includes evaluation of the head, eyes, ears, nose, and throat, and the cardiovascular, dermatological, musculoskeletal, respiratory, and gastrointestinal systems. Breast, genital, and rectal examinations are not required, unless warranted in opinion of the

health care provider. The examination will be performed by a physician, or a nurse practitioner or physician's assistant under the supervision of a physician.

A limited, symptom-directed examination will be performed at all other specified time points, prior to study drug administration (if applicable) or as clinically indicated.

Abnormalities observed at screening will be recorded on the General Medical History and Baseline Conditions page of the eCRF. At subsequent visits, new or worsened clinically significant abnormalities will be recorded on the AE eCRF.

A complete neurologic examination will include the evaluation of consciousness, orientation, cranial nerves, motor and sensory system, coordination and gait, and reflexes. Changes from baseline abnormalities and changes from previous neurological examinations should be recorded at each subsequent neurologic examination. New or worsened abnormalities should be recorded as AEs on the AE eCRF if considered clinically significant.

Physical and neurologic examinations will be collected at the timepoints identified in [Appendix 14.1](#), [Appendix 14.2](#), [Appendix 14.4](#) and [Appendix 14.5](#).

Physical and neurological examinations will not be summarized or listed since exam results are only entered on the General Medical History and Baseline Conditions or AE pages of the eCRF

6.6. Sheehan Suicidality Tracking Scale (S-STS)

The S-STS will be performed at the timepoints identified in [Appendix 14.1](#), [Appendix 14.2](#), [Appendix 14.4](#) and [Appendix 14.5](#).

The S-STS is a brief scale designed to assess and monitor over time the core phenomena of suicidality. The Sheehan-STS is a 16-item scale that will be administered either by a clinician or participant through self-report. Each item in the Sheehan-STS is scored on a 5-point Likert scale (0=not at all, 1=a little, 2=moderately, 3=very, and 4=extremely). Any change in the Sheehan-STS score indicating the presence of suicidality should be immediately evaluated by the investigator and reported to the medical monitor. An AE should only be recorded if the investigator makes an evaluation and deems there to be suicidal ideation or behavior.

Actual results and change from baseline values for the S-STS Total Score will be summarized by visit using descriptive statistics.

All S-STS data will be presented in a data listing.

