2. STUDY OBJECTIVES AND ENDPOINTS

The objectives and endpoints of this study are provided in [Table 1](#) and [Table 2](#).

Table 1: Part 1 (Treatment Period): Study Objectives and Endpoints

	Objective(s)	Endpoint(s)
Primary	The primary objective of the treatment period of the study is to evaluate the safety and tolerability of IV administration of AL001 over 96 weeks in asymptomatic and symptomatic carriers of a GRN mutation causative of FTD and in symptomatic carriers of a C9orf72 mutation causative of FTD.	
Primary Safety Endpoints:
 
To assess the potential effect of cumulative exposure on the safety profile of AL001, the following will be evaluated by dose, such as by using tertiles of the actual dose (normalized to weight) received:
 
 • Incidence, nature, and severity of AEs and SAEs • Incidence of treatment discontinuations and study discontinuations due to AEs • Physical examination abnormalities • Neurological examination abnormalities • Changes in vital signs from baseline over time • Changes in ECGs from baseline over time • MRI abnormalities after dosing relative to baseline • Changes in clinical laboratory tests from baseline over time • Sheehan Suicidality Tracking Scale (Sheehan-STS) • Incidence of ADAs to AL001
Secondary	The secondary objectives of the treatment period of the study are to evaluate the effect of IV administration of AL001 over 96 weeks in asymptomatic and symptomatic carriers of a GRN mutation causative of FTD and in symptomatic carriers of a C9orf72 mutation causative of FTD on the following:	
	
Secondary PK Objective:
 
 • PK 	
Secondary PK Endpoints:
 
 • Serum concentration of AL001 at specified time points • AL001 PK parameters (if data permit) 
 ◦ C_{max} ◦ C_{trough} ◦ AUC_{ss}
	
Secondary PD Biomarker Objectives:
 
 • Longitudinal plasma and CSF PGRN concentration levels • Longitudinal levels of Sortilin in WBCs 	
Secondary PD Biomarker Endpoints:
 
 • The overall change from baseline in PGRN in CSF • The overall change from baseline in PGRN in plasma • The overall change from baseline in Sortilin in WBCs plasma

Table 1: Part 1 (Treatment Period): Study Objectives and Endpoints (Continued)

	Objective(s)	Endpoint(s)

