6.5.10. Sheehan Suicidality Tracking Scale

The Sheehan-STS (described in [Appendix 2](#)) is a brief scale designed to assess and monitor over time the core phenomena of suicidality. Any change in the Sheehan-STS score indicating the presence of suicidality should be immediately evaluated by the investigator and reported to the Medical Monitor. An AE should only be recorded if the investigator makes an evaluation and deems there to be suicidal ideation or behavior.

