8.4.2.9. Sheehan Suicidality Tracking Scale

A summary table for Sheehan-STS Total Score will be presented by time point using descriptive statistics.

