1.2. Study Design

This is a Phase 2, multicenter, open label study evaluating the safety, tolerability, PK, PD, and effect on COAs of AL001 administered intravenously (60 mg/kg, q4w) in asymptomatic and symptomatic carriers of loss-of-function GRN mutations causative of FTD and in symptomatic carriers of C9orf72 hexanucleotide repeat expansion mutations causative of FTD. This study has two parts: A phase 2 open-label treatment period (Part 1), followed by an optional open-label extension (OLE) period (Part 2).

Part 1 is a 96-week evaluation of the safety, tolerability, PK, PD, and clinical effect of AL001 administered intravenously (60 mg/kg, every 4 weeks [q4w]), for a total of 25 doses (96-week dosing period), in asymptomatic and symptomatic carriers of loss-of-function GRN mutations causative of FTD, and in symptomatic carriers of C9orf72 hexanucleotide repeat expansion mutations causative of FTD.

Part 2 is an optional OLE for eligible participants who have completed the 96-week Part 1 treatment period. The OLE period will evaluate the long-term safety and tolerability of AL001 administered at the same dose and regimen as Part 1 (60 mg/kg, q4w), for up to a total of 25 doses (96-week optional OLE period).

Figure 1-1 Overview of Study Schema

Abbreviations: COA, clinical outcome assessment; CSF, cerebrospinal fluid; *GRN*, granulin; IV, intravenous; MRI, magnetic resonance imaging; PD, pharmacodynamic; q4w, every 4 weeks.

2. General Statistical Considerations

All data collected from enrolled participants, excluding screen failures, will be presented in data listings. Data from participants excluded from an analysis set will be presented in the data listings but not included in the calculation of summary statistics for the corresponding analysis set.

Data from Part 1 and Part 2 will be combined and will not be analyzed separately.

For categorical variables, frequencies and percentages will be presented. Continuous variables will be summarized using descriptive statistics (number of participants, mean, standard deviation [SD], median, minimum, maximum, and 90% or 95% confidence interval [CI] where applicable). All summaries will be presented by the three cohorts [asymptomatic FTD-*GRN* (aFTD-GRN), symptomatic FTD-*GRN* (FTD-*GRN*), symptomatic FTD-*C9orf72* (FTD-*C9orf72*)] and All Participants.

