6.1.1. Incidence of Adverse Events

An overall summary of AEs will be presented and will include summaries for the following:

- Any TEAE
- Any Treatment-Related TEAE
- TEAEs by Severity
- Treatment-Related TEAEs by Severity
- Any SAE
- Any Treatment-Emergent SAE
- Any Treatment-Related TESAE
- Any TEAE Leading to Study Drug Discontinuation
- Fatal TESAE

In addition, all TEAEs will be summarized by SOC and PT.

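### Sheehan-STS, a primary safety endpoint, is tabulated only as Total Score statistics by visit; no table counts how many participants worsened on the scale

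*SAP*

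**What the plan says.** Protocol Table 1 and SAP Table 1 list the Sheehan-STS among the Part 1 primary safety endpoints; Table 2 of each document does the same for Part 2. Protocol 8.4.2.9 plans one output: "A summary table for Sheehan-STS Total Score will be presented by time point using descriptive statistics". SAP 6.6 adds change from baseline: "Actual results and change from baseline values for the S-STS Total Score will be summarized by visit using descriptive statistics".

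SAP Section 2 (General Statistical Considerations) fixes what that means: "Continuous variables will be summarized using descriptive statistics (number of participants, mean, standard deviation [SD], median, minimum, maximum", with a confidence interval where applicable. Summaries are by three cohorts (aFTD-GRN, FTD-GRN, FTD-C9orf72) and for all participants.

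Two other routes exist. SAP 6.6 states: "All S-STS data will be presented in a data listing". Under Protocol 6.5.10, a score change that points to suicidality goes at once to the investigator and the Medical Monitor, but "An AE should only be recorded if the investigator makes an evaluation and deems there to be suicidal ideation or behavior". Events recorded that way reach the tables in SAP 6.1.1: "In addition, all TEAEs will be summarized by SOC and PT".

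Both documents describe 16 items, each scored 0 to 4. Neither says how the Total Score is formed.

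**The concern.** For an emergent-suicidality scale, the safety question is how many people got worse and whether the same people did so repeatedly. By-visit statistics of a total score describe the distribution at each visit and do not follow individuals. Rises and falls offset each other in the mean, the median is insensitive to a few people, and the maximum describes one person per visit.

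The SAP reports other safety data at participant level. SAP 6.4 gives the number and percentage with at least one post-baseline abnormal ECG result, plus shifts. SAP 6.2 gives laboratory shifts, and SAP 6.7 gives counts and percentages for anti-drug antibodies. The Sheehan-STS has no such table. At stake is whether the study report can state an incidence for this endpoint without someone deriving it by hand from the listing.

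**Working it through.** **The plan's own figure.** Protocol 8.1 and SAP 2.1 give the probability of at least one clinically significant finding among 40 participants, which is 1 − (1 − p)^40. At p = 0.1%, 1%, 5% and 10% this gives 3.9%, 33.1%, 87.1% and 98.5%, as stated. The figure is not in dispute. It matters here because it is expressed as participants with a finding, and the Sheehan-STS table is not.

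**Inputs.** N = 40 is the planned Part 1 size. A cohort of 20 is the planned ceiling for C9orf72. All change scores below are constructed, because the documents give no Sheehan-STS data.

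**One visit, planned statistics against a count.**

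| Changes at one visit | Mean | SD | Median | Min | Max | Participants with an increase |
|---|---|---|---|---|---|---|
| (a) N = 40: one +4, rest 0 | 0.10 | 0.63 | 0 | 0 | 4 | 1/40 = 2.5% |
| (b) N = 40: two +4, eight −1, rest 0 | 0.00 | 1.01 | 0 | −1 | 4 | 2/40 = 5.0% |
| (c) N = 20: one +12, one −12, rest 0 | 0.00 | 3.9 | 0 | −12 | 12 | 1/20 = 5.0% |

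Means: (a) 4/40 = 0.10; (b) (8 − 8)/40 = 0; (c) (12 − 12)/20 = 0. SD in (c): √(288/19) = 3.9. From (a) to (b) the number who worsened doubles, yet the mean falls and the maximum does not move. In (c) the minimum, maximum and SD do show that something happened.

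**Two visits.** Take N = 40 with all other changes 0. If participant A rises by 4 at both visits, each visit shows mean 0.10 and maximum 4. If A rises by 4 at the first visit only and participant B at the second only, each visit shows the same mean and maximum. The by-visit tables are identical, but the counts of people affected are 1/40 and 2/40.

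**Number of visits.** The schedules give the scale at Visits 2 to 26 in Part 1 (25 visits after the first dose) and Visits 27 to 51 in Part 2 (25 more). Each by-visit row covers only those assessed at that visit. SAP Section 2 itself reports high attrition, so someone who worsens and then leaves is missing from later rows. Analysis windows are announced only for clinical outcome and biomarker analyses, so it is not stated how an unscheduled Sheehan-STS enters the table.

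**Precision of a count.** Exact 95% limits are the 2.5% point of Beta(x, n − x + 1) and the 97.5% point of Beta(x + 1, n − x); for x = 0 the upper limit is 1 − 0.025^(1/n).

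| Count | % | Exact 95% CI |
|---|---|---|
| 0/40 | 0 | 0 to 8.8% |
| 1/40 | 2.5 | 0.06 to 13.2% |
| 2/40 | 5.0 | 0.6 to 16.9% |
| 0/20 | 0 | 0 to 16.8% |
| 1/20 | 5.0 | 0.1 to 24.9% |

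**The case against.** The strongest reply is that nothing is hidden. The planned table prints the SD, minimum and maximum, so a single large rise shows, as in example (c). Every score is listed, and with about 40 participants the listing can be read. Score changes that point to suicidality must be evaluated at once, and those judged to be ideation or behavior are counted by participant in the TEAE tables. An independent committee reviews Part 1 safety data. The SAP also follows the summary that the protocol specifies.

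Most of this stands. A reader might infer that the endpoint is summarised by its mean alone, or that the plan is all but blind to emergent suicidality. The documents support neither, for the reasons just given. Nor do they say that most participants score zero, or that the total runs from 0 to 64.

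What the reply leaves open is the count. A maximum does not say how many rose or whether they were the same people. The AE table holds only cases that the investigator confirmed, so a rise not so judged is counted in no table. A listing is not a summary of a primary safety endpoint.

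A second objection also stands in part. Neither document equates a total above zero, or any increase, with ideation or behavior. A worst value over 25 to 50 visits, without a control group, will pick up small fluctuations. That limits how the count is labelled and argues against displacing the planned summary.

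**Conclusion.** The gap is real but narrow. A primary safety endpoint has no participant-level table based on the scale, although the SAP gives counts or shifts for ECG, laboratory and antibody results. The planned statistics can show that a rise occurred; they cannot show how many people rose or whether the same person recurred. In the constructed cases, 1/40 and 2/40 give the same maximum and median, with means of 0.10 and 0.00.

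This rests on illustrative scores and on planned sizes of 40 overall and up to 20 in a cohort. The GRN cohort is split in the SAP, so its two groups will be smaller and a single rise will move their means more. The conclusion does not depend on the range of the total score. It does not mean that confirmed suicidality would go unreported.

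**What to change.** Add to SAP 6.6, by cohort and overall:

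- the number (%) of participants with Total Score 0 at baseline and above 0 at any post-baseline assessment;
- the number (%) with any increase over baseline, taking the worst post-baseline value and including unscheduled assessments;
- exact 95% confidence intervals for both.

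Report these beside the planned by-visit statistics, not in their place. Label them as score increases, not as confirmed ideation or behavior. State the rule that forms the Total Score from the 16 items.

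The cost is one more table from data already collected, with no change to sample size, visits or procedures. The downside is that a worst-case count over many visits will include some small fluctuations, and a footnote should say so. This is a cheap improvement.

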6.7. Immunogenicity

Immunogenicity sample collection for ADA will be collected at the timepoints indicated in [Appendix 14.1](#), [Appendix 14.2](#), [Appendix 14.3](#), [Appendix 14.4](#) and [Appendix 14.5](#). Additional unscheduled assessments for participants with signs and symptoms of infusion-related reactions may be collected.

Antidrug antibody results will be summarized by visit using the frequency count and percentage of participants in each result category, as well as descriptive statistics of ADA titer by visit. The summary of ADA results will not include unscheduled assessments for participants with signs and symptoms of infusion-related reactions. Instead, data at baseline and the following visits for subjects with signs and symptoms will be listed separately. All immunogenicity data will be presented in a data listing.

6.8. Magnetic Resonance Imaging

Magnetic resonance imaging assessments will be performed at the timepoints indicated in [Appendix 14.1](#), [Appendix 14.2](#), [Appendix 14.4](#) and [Appendix 14.5](#).

MRI scans of the brain will be performed and centrally reviewed for assessment of safety (structural images). The safety assessment on MRI scans will be presented in a data listing.

7. Pharmacokinetics

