8.4.2.4. Adverse Events

Adverse events will be recorded as described in [Section 7.7](#) and will be coded to system organ class and preferred term according to MedDRA, Version 21.1 or later. A TEAE is defined as described in [Section 7.1](#). The following AE summaries will be reported by system organ class, preferred term, and combined participant status and dementia type at baseline:

- TEAEs
- Treatment-related TEAEs
- TEAEs by relationship to study drug
- TEAEs by severity
- SAEs
- TEAEs leading to study drug discontinuation
- TEAEs leading to study discontinuation

For safety reporting, any clinically significant changes in MRI after dosing relative to baseline will be evaluated by the investigator and will be included in the eCRF as AEs. A separate analysis of AEs identified through MRI will not be conducted.

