1.1. Objectives and Endpoints

Table 1: Part 1 (Treatment Period): Study Objectives and Endpoints

	Objective(s)	Endpoint(s)
Primary	The primary objective of the treatment period of the study is to evaluate the safety and tolerability of IV administration of AL001 over 96 weeks in asymptomatic and symptomatic carriers of a GRN mutation causative of FTD and in symptomatic carriers of a C9orf72 mutation causative of FTD.	Primary Safety Endpoints: To assess the potential effect of cumulative exposure on the safety profile of AL001, the following will be evaluated by dose, such as by using tertiles of the actual dose (normalized to weight) received: 
• Incidence, nature, and severity of AEs and SAEs• Incidence of treatment discontinuations and study discontinuations due to AEs• Physical examination abnormalities• Neurological examination abnormalities• Changes in vital signs from baseline over time• Changes in ECGs from baseline over time• MRI abnormalities after dosing relative to baseline• Changes in clinical laboratory tests from baseline over time• Sheehan Suicidality Tracking Scale (Sheehan-STS)• Incidence of ADAs to AL001
Secondary	The secondary objectives of the treatment period of the	

	
study are to evaluate the effect of IV administration of AL001 over 96 weeks in asymptomatic and symptomatic carriers of a GRN mutation causative of FTD and in symptomatic carriers of a C9orf72 mutation causative of FTD on the following:
	
	
Secondary PK Objective:
 
 • PK 	
Secondary PK Endpoints:
 
 • Serum concentration of AL001 at specified time points • AL001 PK parameters (if data permit) ◦ C_{max} ◦ C_{trough} ◦ AUC_{ss}
	
Secondary PD Biomarker Objectives:
 
 • Longitudinal plasma and CSF PGRN concentration levels • Longitudinal levels of Sortilin in WBCs 	
Secondary PD Biomarker Endpoints:
 
 • The overall change from baseline in PGRN in CSF • The overall change from baseline in PGRN in plasma • The overall change from baseline in Sortilin in WBCs in plasma

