Adverse Events will be coded by SOC and PT according to MedDRA, version to be delineated in the CSR.

All summary tables will include counts and frequency of participants and number of events. Subject incidence rate of AEs will be summarized by SOC and PT and for PT only. The summary will be provided separately by overall descending incidence rate and then by alphabetical order. A separate summary will be provided by alphabetical order for SOC and PT. A participant with 2 or more occurrences for the same AE, the subject will be counted only once in that level using the worst severity (for the severity table) or the most related (for the relationship to study drug table). Percentages will be based upon the number of participants in the Safety population.

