10.3. Brain Imaging

Brain imaging including structural MRI and DTI assessments will be performed at the timepoints indicated in [Appendix 14.1](#), [Appendix 14.2](#), [Appendix 14.4](#) and [Appendix 14.5](#).

Brain imaging measurements include:

- Regional brain volumes as measured by MRI
- Diffusion fractional anisotropy (FA) in Corpus Callosum only as measured by DTI

Actual results and percent change from baseline values for quantitative MRI (frontotemporal, parietal, and subcortical regions only) and FA parameters will be summarized by visit using descriptive statistics. Mean and median percent change from baseline values, the standard deviation, minimum and maximum will also be presented in a plot.

All MRI and DTI data will be presented in data listings.

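### The primary endpoint on MRI abnormalities gets only a data listing, so no identifiable incidence of MRI findings relative to baseline is reported

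*SAP*

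**What the plan says.** Tables 1 and 2 of the protocol, repeated as Tables 1 and 2 in SAP 1.1, include "MRI abnormalities after dosing relative to baseline" among the primary safety endpoints of Part 1 and the primary endpoints of Part 2. For Part 1 the list opens by saying that "the following will be evaluated by dose, such as by using tertiles of the actual dose (normalized to weight) received".

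SAP 6.8 sends the structural scans to central review for safety and then gives the whole analysis in one sentence: "The safety assessment on MRI scans will be presented in a data listing".

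Protocol 8.4.2.4 adds a second route, entry as an adverse event: "any clinically significant changes in MRI after dosing relative to baseline will be evaluated by the investigator and will be included in the eCRF as" (the sentence ends by naming adverse events). It then sets a limit: "A separate analysis of AEs identified through MRI will not be conducted". Under SAP 6.1 those events join the general tables: "Subject incidence rate of AEs will be summarized by SOC and PT and for PT only".

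SAP 10.3 also analyses MRI: "Actual results and percent change from baseline values for quantitative MRI (frontotemporal, parietal, and subcortical regions only) and FA parameters will be summarized by visit". That concerns regional volumes and fractional anisotropy as exploratory pharmacodynamic measures, not the safety read.

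SAP Section 12 says that safety MRI will be reported under Sections 8.8 and 12.2. Neither section exists in this SAP; the MRI text is in 6.8 and 10.3.

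**The concern.** The endpoint is defined by comparison with baseline, and a central reader supplies the data for it. Yet no planned output compares the reads with baseline or counts participants. A listing shows every read, but it does not define what is new or worsened, who belongs in the denominator, or how many participants had a finding.

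The adverse event route covers only part of the gap. It depends on the site investigator's judgement, and an event found on MRI carries no mark of how it was found. A reader of the study report who asked how many participants developed a new brain MRI finding on treatment would find no table that answers the question, overall or by cohort. The by-dose evaluation that SAP Table 1 attaches to this endpoint has no count to work from either.

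**Working it through.** **1. The plan's own figure.** Protocol 8.1 and SAP 2.1 give the chance of seeing at least one finding among 40 participants. The formula is 1 − (1 − p)^40:

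- p = 0.1%: 3.9%
- p = 1%: 33.1%
- p = 5%: 87.1%
- p = 10%: 98.5%

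All four agree with the documents. The point below does not dispute them.

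**2. From endpoint to output.** The primary safety endpoints set against the summaries that the SAP plans:

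| Endpoint | Planned summary |
|---|---|
| Adverse events | Participant incidence by system organ class and preferred term (6.1) |
| Laboratory tests | Change from baseline and shift tables (6.2) |
| Vital signs | Change from baseline (6.3) |
| ECG | Change from baseline, shift table, counts beyond thresholds (6.4) |
| Physical and neurological examinations | None; stated with a reason in Section 12 |
| Sheehan-STS | Change from baseline (6.6) |
| Anti-drug antibodies | Counts and percentages by visit (6.7) |
| MRI abnormalities | None; listing only (6.8) |

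MRI and the examinations are the two data types with no summary of their own. The SAP states and explains this only for the examinations.

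**3. Following a finding through the plan.**

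- *New finding, judged clinically significant by the investigator* (protocol 8.4.2.4; protocol 7.3 adds findings that require treatment or discontinuation). It becomes an adverse event and is counted under its preferred term. The percentage is taken over the Safety population, which is everyone dosed, including anyone never scanned again. It cannot be told apart from the same term reached by another route.
- *New finding below that bar.* It appears in the listing and is counted nowhere.
- *Finding already present at baseline and unchanged.* It also appears in the listing. Separating it from the previous case is left to the reader.

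**4. Volume.** Post-baseline scans are scheduled at Weeks 25, 49, 73, 97, 145 and 197. The ceiling is 6 × 40 = 240 reads to compare by hand. It would be reached only if all 40 participants completed both parts, and SAP Section 2 reports high attrition.

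**5. What a count would carry.** For zero events the exact (Clopper-Pearson) two-sided 95% upper limit is 1 − 0.025^(1/n):

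- n = 40 (planned total): 1 − 0.9119 = 8.8%
- n = 20 (cap for each mutation cohort): 1 − 0.8316 = 16.8%
- n = 10 (assumed, to show a mutation cohort at its cap reduced by half): 1 − 0.6915 = 30.8%

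For assumed non-zero counts, from the beta quantiles: 2/40 gives 0.6% to 16.9%, and 4/40 gives 2.8% to 23.7%. The event counts are illustrations, not predictions.

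**The case against.** The best defence is that the endpoint is not worded as an incidence. The same list uses that word for adverse events, discontinuations and anti-drug antibodies, but not for MRI. In an open-label study of about 40 participants with no formal testing, a full listing plus the adverse event tables is reporting of a kind, and a patient reader could count from the listing. This is fair: the endpoint is reported weakly, not left out. But such a reader would have to choose the rule for new or worsened, and the denominator, after seeing the data. SAP Section 1 would class that as post hoc.

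Three stronger readings are tempting, and the documents do not support them.

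- *That the protocol forbids a separate MRI analysis.* Protocol 8.4.2.4 excludes only a separate analysis of adverse events identified through MRI. It does not bar a table of central reads, and quantitative MRI is summarised by visit as an exploratory measure.
- *That the endpoint has no numerator, denominator or baseline comparison at all.* Clinically significant changes have all three inside the treatment-emergent tables: participant counts, percentages of the Safety population, and a definition that requires an event to be new or worse after exposure. They lack any mark of being MRI findings.
- *That SAP Section 12 conceals a dropped analysis.* Protocol 8.4.2 never planned a summary of central safety reads, so there was none to declare as dropped. The examinations differ: protocol 8.4.2.5 planned shift tables, and Section 12 records their removal.

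**Conclusion.** The point holds in a limited form and should be fixed before database lock. The only MRI-specific safety output for this primary endpoint is a listing. Clinically significant changes are counted but cannot be identified as MRI findings, and lesser central-read findings are not counted. The mismatch between the endpoint table and the analysis section is in both documents; it is not something that the SAP introduced.

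This conclusion rests on reading the documents together, not on arithmetic. The upper limits of 8.8% and 16.8% only illustrate what a zero count would convey. They assume that every participant has a baseline and a post-baseline scan, so they are the tightest attainable. The 20 is an enrolment cap, and on the *GRN* side it pools two of the SAP's three reporting cohorts, so limits for those two would be wider. The documents do not show how the central reads are recorded, so it is not known whether comparison with baseline is already coded.

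**What to change.** In SAP 6.8, keep the listing and add one table: n/N (%) of participants with any new or worsened central-read safety MRI finding against the baseline scan, by finding type, by cohort and overall. Define N as participants with a baseline and at least one post-baseline scan. State which scan is the baseline where the screening scan was waived because one from AL001-1 was available within 3 months (protocol 6.2).

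In SAP Section 12, change the MRI references from Sections 8.8 and 12.2 to 6.8 and 10.3. If a listing alone is what the sponsor intends, Section 12 should say so and give the reason.

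The sentence in protocol 8.4.2.4 can stay, because a table of central reads is not an analysis of adverse events. No new assessment is needed. The cost is one extra table, and some coding of reads as new or worsened if the central reader does not already supply it.
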